8. SAFETY REPORTING

The reporting and documentation of AEs and clinically significant laboratory abnormalities or other assessments is an essential component of all clinical studies. Therefore, it is important that all investigational staff understand the requirements and responsibilities outlined below. It is the responsibility of the Investigator to ensure that all AEs and other clinically significant findings that occur during the conduct of a clinical study are documented and reported accurately.

Adverse event(s) should be documented in terms of a medical diagnosis(ies) where possible, rather than signs and/or symptoms.

8.1 Adverse Event Definitions

8.1.1 Adverse Event (AE)

At each evaluation the investigator will determine whether any AEs have occurred by asking a non-leading question and/or reviewing the diary card. Follow-up of any AEs that occur will be conducted according to standard local practice.

An AE includes any untoward medical occurrence in a study participant who uses the investigational product (whether it is the investigational product or the placebo) and which does not necessarily have a causal relationship to the study product (whether it is the investigational product or the placebo).

The investigator will make a judgment regarding whether or not, in their opinion, the AE was related to the test product. However, even if the investigator feels there is no relationship to the test product, the AE must be reported. If any clinical AEs have occurred they will be recorded on the AE report page of the CRF and their intensity will be graded.

AEs may include:

- 1. The significant worsening of a disease or symptoms of a disease following administration of investigational product/drug.
- 2. An intercurrent illness with an onset after use of the investigational product.
- 3. Exacerbation (i.e., increase in frequency or intensity) of a pre-existing condition or event.

An AE does not include a/an:

- 1. Medical or surgical procedure: the condition that leads to the procedure is an AE.
- 2. Situations where an untoward medical occurrence has not occurred (e.g. hospitalization for cosmetic/elective surgery, social and/or convenience admissions).
- Overdose of either study drug or concomitant medication that does not result in any signs
 or symptoms. If any signs or symptoms of an overdose present, then these will be
 recorded as an AE.

8.1.2 Serious Adverse Event (SAE)

An SAE is defined as any adverse drug experience occurring at any dose¹ that results in any of the following outcomes:

- Results in death²
- Is life-threatening³
- Requires in-patient hospitalization or prolongation of existing hospitalisation⁴
- Results in persistent or significant disability / incapacity
- Is a congenital anomaly / birth defect

- ¹ **Occurring at any dose**: Does not imply that the participant is using the study product at the time of the event. Use may have been interrupted temporarily prior to the onset of the SAE, but may have contributed to the event.
- ² **Death**: Death is an outcome of an SAE, and not an SAE in itself. All deaths must be reported for participants on study and for deaths occurring within 30 days of last study drug dose or within 30 days of last study evaluation, whichever is longer, to Starpharma Regulatory and QA Departments, who in turn will ensure immediate (within 24 hours) reporting to all appropriate regulatory bodies within the required timelines. The investigator should supply Starpharma and the IEC / IRB with any additional requested information as available (e.g. autopsy reports and terminal medical reports).
- ³ **Life-threatening**: The term "life-threatening" in the definition of "serious" refers to an event in which the participant was at immediate risk of death at the time of the event. It does not refer to an event which hypothetically might have caused death if it were more serious.
- ⁴ **Hospitalization**: This is defined as the participant being hospitalized overnight, or the participant's hospital stay being prolonged for at least an additional overnight stay. Hospital admissions for a pre-existing condition (e.g. elective surgery) or for normal disease management procedures (e.g. chemotherapy) will not be considered as serious. Complications that occur during hospitalizations are AEs. If a complication prolongs hospitalization, it is an SAE.

Important medical events that may not result in death, be life-threatening, or require hospitalization may be considered a serious adverse event (SAE) when, based upon appropriate medical judgment, they may jeopardize the study participant and may require medical or surgical intervention to prevent one of the outcomes listed in this definition. Examples of such medical events include allergic bronchospasm requiring intensive treatment in an emergency room or at home, blood dyscrasias or convulsions that do not result in inpatient hospitalization, or the development of drug dependency or drug abuse.

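### Footnote 4 of the SAE definition (8.1.2) can be read to exempt an unplanned admission for worsening of a pre-existing condition, which does not fit the AE definition in 8.1.1

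*Protocol*

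**What the plan says.** Three statements in section 8 of the protocol bear on this point.

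- **What is an AE (8.1.1).** The list of what AEs may include has "The significant worsening of a disease or symptoms of a disease following administration of investigational product/drug" and "Exacerbation (i.e., increase in frequency or intensity) of a pre-existing condition or event". The list of what an AE is not includes "Situations where an untoward medical occurrence has not occurred (e.g. hospitalization for cosmetic/elective surgery, social and/or convenience admissions".
- **What is serious (8.1.2).** One of the listed outcomes is "Requires in-patient hospitalization or prolongation of existing hospitalisation".
- **Footnote 4 to that outcome (8.1.2).** It defines hospitalization as an overnight stay, or a stay prolonged by at least one more night, and then says "Hospital admissions for a pre-existing condition (e.g. elective surgery) or for normal disease management procedures (e.g. chemotherapy) will not be considered as serious". It goes on to say that complications during a hospital stay are AEs, and "If a complication prolongs hospitalization, it is an SAE".

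A separate paragraph of 8.1.2 lets important medical events be classed as serious on medical judgment.

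**The concern.** The AE definition and the seriousness footnote draw their exclusions differently. Section 8.1.1 excludes admissions only where nothing untoward has happened. Footnote 4 excludes admissions by the type of condition treated, and does not ask whether the condition has changed since the woman began the gel. A site that applies the footnote as written could treat an unplanned admission for an exacerbation as non-serious, while another site, reading it alongside 8.1.1, would report the same event as an SAE.

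The seriousness label has consequences. Under 8.2.2 every SAE, related or not, goes to the sponsor within 24 hours of the investigator becoming aware of it. Under 8.10 all SAEs are reported to the study team on an ongoing basis. Under 10.10 SAEs have their own summary and listing. In a multi-center trial these should not depend on which reading a site adopts.

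**Working it through.** No arithmetic applies; the protocol gives no figure on this point. The check applies the text to a test case: a participant has a condition recorded at entry, it worsens after first use of gel, and she has an unplanned overnight admission for it.

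1. **Is it an AE?** Yes. Section 8.1.1 names both significant worsening of a disease after product and exacerbation of a pre-existing condition. The exclusion for "hospitalization for cosmetic/elective surgery, social and/or convenience admissions" does not apply, because something untoward did occur.
2. **Does it meet a seriousness criterion?** Yes. It required in-patient hospitalization, and the stay was overnight, as footnote 4 requires.
3. **Does footnote 4 take it out again?** On its words it can. The admission is for a pre-existing condition. Elective surgery is introduced as an example and does not define the class. Nothing in the footnote refers to planning or to an unchanged condition.
4. **Do the other routes in 8.1.2 bring it back?** Only in part.
   - Death, life-threatening events, persistent or significant disability and congenital anomaly remain, but the test case need not meet any of them.
   - The rule on complications covers events that arise during a stay and prolong it. It does not cover the event that caused the admission.
   - The important-medical-event paragraph is permissive: such an event may be considered serious.
5. **Does 8.10 catch it if it is not an SAE?** In some cases. Genital irritation at Grade 2 or above is reported on an ongoing basis, and so are other AEs at Grade 3 or above if potentially related to product. An exacerbation of a non-genital condition judged unrelated falls under neither, and would reach that list only as an SAE.
6. **What is lost, and what is kept?** The event stays on the AE page (8.3), in the TEAE summaries and in the by-subject listing of all AEs (10.10). It can miss the 24-hour report and the SAE summary. Faster regulatory reporting under 8.2.2 is affected only if the event is also drug-related and unexpected.

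The case can arise in this trial. Every participant enters with BV (5.1.1), and 7.2.1.2 provides for recording ongoing medical conditions and relevant ones from the previous 5 years.

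**The case against.** The strongest answer is that the sections can be read in harmony. The footnote's only example for this limb is elective surgery, and 8.1.1 uses the same example for admissions without an untoward occurrence. Section 8.5 defines Baseline, for monitoring toxicities, as the status before first use of product and manages changes from it. Read together, an exacerbation is a new AE, its admission meets the hospitalization criterion, and footnote 4 is left to cover planned admissions for an unchanged condition. That reading is available, and is probably what was meant. It does not settle the matter, because 8.1.1 decides what is an AE and not what is serious, and the limiting words in 8.1.1 are absent from the footnote.

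Other parts of the answer stand in full and limit the point.

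- **That such admissions are never serious and escape SAE reporting.** A reader might infer this, but the text does not say so. It neither says never nor mentions BV or unplanned admissions; it permits that outcome without requiring it. The footnote qualifies only the hospitalization criterion, and the other routes stay open.
- **That worsened BV would miss expedited reporting.** This is a weak example. Section 8.3 says ineffective treatment is not to be considered causally related, so BV that worsens through lack of effect would not be expedited even if serious.
- **That product-related genital harm would go unseen.** The 8.10 reporting of genital irritation at Grade 2 or above would very likely catch a case severe enough for admission, and 8.5 and 16.3 provide for holding product in response to non-serious AEs as well.
- **That all 132 women are exposed to the gap.** All have BV at entry, but the protocol gives no rate of overnight admission for it. Participants must be healthy apart from BV, and section 2.6 reports no SAEs in five completed studies, although section 2.7 notes that those excluded symptomatic BV.

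**Conclusion.** The point holds as an ambiguity in a stated rule. Applied as worded, footnote 4 can remove the seriousness label from an event that is an AE under 8.1.1 and meets the hospitalization criterion of 8.1.2. This is more than a missing detail, since following the sentence literally can misclassify an event.

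Its practical size is small. The documents give no admission rate. If one assumes 0 to 2 overnight admissions for any reason in 5-6 weeks, the number due to an exacerbated pre-existing condition is at most that and may well be none. Should exactly one occur, with no other SAE, the SAE count would be 1 under the harmonized reading and 0 under the literal one. That count is hypothetical. The primary endpoint, sample size, significance levels and analysis datasets are not affected.

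**What to change.** Reconcile footnote 4 with 8.1.1 in two steps:

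- Limit the exclusion to elective or pre-planned admissions for a condition that has not worsened since first use of study product.
- State that an unplanned admission for worsening of a pre-existing condition meets the hospitalization criterion.

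Carry the same wording into the instructions for the SAE form so that all sites classify alike. The change concerns reporting classification only and alters no treatment or management rule. It costs a sentence or two in 8.1.2, the matching form instruction, and possibly one or two more SAE forms.

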8.1.3 Unexpected Adverse Drug Reaction (UADR)

Unexpected Adverse Drug Reaction is defined as an adverse reaction to study drug that is not identified in nature, severity or frequency in the IB or that is not expected from the characteristics of study drug.

8.2 Reporting of an Adverse Event

8.2.1 Timeframe for Reporting Adverse Events

AE reporting will begin from first dose and will continue throughout the study until the TOC visit. AEs occurring during the screening phase of the study and before administration of study product are to be reported in the Screening Signs and Symptoms section of the CRF. AEs occurring thereafter (*i.e.* after first administration of study product) are to be reported in the AE reporting pages of the CRF.

8.2.2 Timeframe and Timelines for Reporting Serious Adverse Events

SAE reporting will begin from consent and will continue until 30 days post last dose of study medication.

ANY SERIOUS ADVERSE EVENT (INCLUDING DEATH) DUE TO ANY CAUSE WHICH OCCURS DURING THE COURSE OF THE INVESTIGATION, WHETHER OR NOT RELATED TO THE STUDY PRODUCT, MUST BE REPORTED IMMEDIATELY (within 24 hours of the investigator becoming aware of the event) TO STARPHARMA REGULATORY & QA DEPARTMENT AS FOLLOWS:

Reporting Contact: VP Development and Regulatory Affairs or Delegate

XXXXXXXXXXXX

XXXXXXXXXXXX

Telephone contact must be made with either Starpharma or study monitor in order to make an initial SAE report. Specific contact details and 24-hour contact details are available in the Study Procedures Manual.

The Investigator (or delegate) will be requested to complete Starpharma's SAE form including as much information regarding the event that is available at the time of the initial report. Investigators should not wait to receive additional information to fully document the event before notifying Starpharma of an SAE.

The Principal Investigator or Co-Investigator must review and sign-off each SAE report to confirm that they have reviewed the SAE and the details are correct; however, this sign-off must not delay the initial reporting of the SAE and may be undertaken after the initial report has been made.

Prompt notification is essential so that legal requirements and ethical obligations to the participants participating in the study can be met. A telephone report must be followed by a written report including copies of relevant medical records, autopsy reports and other relevant documents.

When reporting SAEs, the investigator should not include the name or address of the individual participant.

Minimum requirements for SAE reporting:

- Protocol number
- Center name/ID
- Reporting Investigator's/physician's name
- Participant initials, randomization number, age and sex

- Study drug dose and duration of treatment
- Condition treated (medical diagnosis, if known)
- Nature and severity of the SAE
- Relationship of SAE to Study drug
- Potentially confounding factors/concomitant medication*
- Action taken/outcome*
- * Where action was taken or concomitant medication was administered, ensure that corresponding CRF pages have been completed.

The investigator must also:

- Report all SAEs to the reviewing IEC / IRB within the time-line specified by the reviewing body;
- Submit follow-up reports to Starpharma until the SAE has resolved or, in the case of permanent impairment, until the SAE stabilizes.

If the SAE is study drug related and unexpected, the SAE will be reported by Starpharma to the regulatory authority(ies) within required timeframes (i.e. within 7 (fatal or life-threatening) or 15 (non-fatal or not life-threatening) calendar days of the event occurring and/or becoming aware of the event).

8.3 Recording an Adverse Event

- Adverse events: All adverse events are to be recorded on the 'Adverse Event' pages within the participant's CRF.
- Serious Adverse Events: In addition to the 'Adverse Event' page, SAEs are to be recorded on Starpharma Serious Adverse Event reporting form and then a copy is inserted into the study participant's CRF.

At each clinical evaluation the Investigator/delegate will determine whether any AEs have occurred. The participant will be questioned in a non-leading way and no specific symptoms will be suggested. If known, the medical diagnosis of an AE should be recorded in preference to the listing of individual signs and symptoms.

All AEs deemed to be signs of genital irritation will be identified by the Investigator as such in the CRF by checking a check-box and additionally will be noted as either being reported by participant (either spontaneously or in the diary card) or detected at pelvic/genital exam. Signs and symptoms of genital irritation are defined as follows:

Symptoms:

Pelvic pain; vaginal and vulvar pain; tenderness; vulval itching, edema, erythema, lesions (vesicles, blisters, erosions, ulcers), or rash; vaginal itching, dryness, excessive discharge; dysuria; vulvovaginitis; or dyspareunia.

Signs:

Vulval edema, erythema, lesions (vesicles, blisters, erosions, ulcers), or rash; vaginal edema, erythema, excessive discharge or lesions; cervical edema, erythema, discharge, or lesions; vulvovaginitis; or cervicitis.

The Investigator will make a judgment regarding whether or not, in his/her opinion the study product had any possible causal relationship to the AE. The Investigator will evaluate any changes in laboratory values, and make a determination as to whether or not the change is clinically important, and whether or not the changes were related to the study drug. However, even if the Investigator feels there is no relationship to the study drug, the AE must be recorded in the CRF.

Every AE must be assessed and the CRF entry reviewed and confirmed by the Principal Investigator or Co- or Sub-Investigator. This confirmation is indicated by an Investigator sign-off in the CRF.

If any AEs are present when a participant completes the study or when a participant is withdrawn from the study, the Investigator/delegate should make every effort to follow-up the participant until the AE has resolved or stabilized. All follow-up information (and attempted follow-up contacts) should be documented in the participant's medical records.

The severity of an AE experienced by the participant is graded in the first instance according to the Division of AIDS Female Genital Grading Table for Use in Microbicide Studies (Version 1.0 (Addendum 1) November 2007). Events not listed in the Female Genital Grading Table will be graded according to The Division of AIDS Table for Grading the Severity of Adult and Pediatric Adverse Events (Version 1.0, December 2004).

If an AE changes in severity, it should be a single entry in the CRF, and assigned the highest severity experienced.

Those AEs not covered within either of the above toxicity tables will be graded as follows:

Grade 0: None Not an AE

Grade 1: Mild An AE that causes no or minimal interference with usual social

and functional activities.

Grade 2: Moderate An AE that causes greater than minimal interference with usual

social and functional activities

Grade 3: Severe An AE that causes inability to perform usual social and

functional activities.

Grade 4: Life Threatening An AE that causes inability to perform basic self-care functions

or medical or operative intervention is indicated to prevent

permanent impairment, persistent disability or death.

It should be noted that an AE that is considered to be "severe" may not necessarily be considered to be "serious" or of major medical significance.

The relationship to study product should be assessed using the following definitions:

Not Related The adverse event is clearly explained by another cause not

related to the study product.

Probably Not Related A potential relationship between study product and the adverse

event could exist (i.e. the possibility cannot be excluded), but the adverse event is most likely explained by causes other than the

study agent.

Possibly Related The adverse event and administration of study product are

reasonably related in time, and the adverse event can be explained equally well by causes other than the study product.

Probably Related The adverse event and use of study product are reasonably related

in time, and the adverse event is more likely explained by study

product than other causes.

Definitely Related The adverse event and use of study product are related in time,

and a direct association can be demonstrated.

It should be emphasized that ineffective treatment should not be considered as causally related in the context of AE reporting.

These criteria in addition to good clinical judgment should be used as a guide for determining the causal assessment.

The degree of certainty with which an AE is attributed to study product or alternative cause, (*e.g.* natural history of the underlying diseases, concomitant therapy, etc.) will be determined by how well the event can be understood in terms of:

- Known pharmacology of the product;
- Reaction of a similar nature previously observed with similar products;
- The event having often been reported in literature for similar products as product related;
- The event being related by time to product use/termination, product withdrawal, or reproduced on rechallenge.

8.4 Clinical Laboratory Abnormalities and Other Abnormal Assessments as AEs or SAEs

Laboratory abnormalities such as an abnormal urinalysis deemed not clinically significant and not considered an AE according to the DAIDS toxicity tables are usually not recorded as AEs or SAEs. However, all abnormal laboratory findings or other abnormal assessments (e.g. pelvic

exam) that meet the definition (or cause signs and symptoms that meet the definition) of an AE (or SAE) must be reported as outlined above.

8.5 Toxicity Management

AEs and laboratory abnormalities will be graded as outlined in Section 8.3.

For the purpose of monitoring toxicities, Baseline is defined as the status or last value prior to the first use of study product. All management is based on changes from this initial status or value.

All grade 2 or higher laboratory abnormalities should be confirmed by repeat testing as soon as possible, preferably within 3 calendar days of receipt of results prior to dose interruption or discontinuation, unless such a delay is not consistent with good medical practice.

Study participants will be asked to contact the study site staff if they miss a dose of study medication due to an AE. Site staff will assess whether the participant should come in for an assessment, and if so, an ad hoc visit will be scheduled as soon as possible. In response to AEs reported by participants and/or observed upon exam by study staff, the study site investigator or designee will recommend either continuation or holding study product use consistent with the criteria in Section 16.3. Study product use also will be held or discontinued in the event of an SAE that is judged by the site Investigator or designee to have a potential causal relationship with study product.

Unless the participant withdraws consent, they will remain in the study to complete the safety evaluations (unless clinically contraindicated according to Table 1 and Section 16.3).

Participants requiring treatment for an STI will be withdrawn from the study. Participants who develop any other conditions requiring vaginal therapy (*e.g.* candidiasis) whilst on study where oral therapy cannot be used or antibiotics by any route, will cease study product, however they should continue with the remaining study visits.

